## 10.0 ANCILLARY TREATMENT/SUPPORTIVE CARE

**10.1 Antiemetics:** Since TMZ may cause nausea, it is suggested that an appropriate antiemetic (e.g., 1 mg dose of granisetron, or 4 mg of ondansetron, or other) be given one hour before

TMZ. As an alternative, antiemetic may be used on the first 3 days of concomitant RT/TMZ and the first 3 days of adjuvant TMZ, with any further need determined by the treating physician based on perception of clinical need. Additional symptoms will be managed as per standard antiemetic guidelines.

**10.2 Antidiarrheals:** Use of loperamide (Imodium) for treatment-induced diarrhea is strongly encouraged. Treat diarrhea promptly with appropriate supportive care, including loperamide. Instruct patients to begin taking loperamide at the first signs of: 1) poorly formed or loose stool, 2) occurrence of more bowel movements than usual in one day, or 3) unusually high volume of stool. Loperamide should be taken in the following manner: 4 mg at first onset of diarrhea, then 2 mg after each unformed stool. Daily dose should not exceed 16 mg/day. Loperamide should not be taken prophylactically. Advise patients to drink plenty of clear fluids to help prevent dehydration caused by diarrhea. Avoid loperamide if there is the presence of blood or mucus in the stool or if diarrhea is accompanied by fever.

**10.3 Supportive care:** Patients should receive full supportive care while on this study. This includes blood product support, antibiotic treatment, and treatment of other newly diagnosed or concurrent medical conditions. All blood products and concomitant medications (i.e., antidiarrheals, analgesics, antiemetics) received from the first day of treatment until 30 days after the final dose will be recorded on the concomitant medication form. Adequate hydration should be maintained in the setting of dysgeusia (popsicles and Gatorade have been found to be useful by some investigators).

**10.4 Colony stimulating factors:** These factors should not be used prophylactically to prevent granulocytopenia. Growth factors are not permitted to induce elevations in neutrophil count for the purposes of (1) administration of TMZ on the scheduled dosing interval, or (2) allowing treatment with TMZ at a higher dose, or (3) avoiding interruption of the treatment during concomitant radiotherapy. The therapeutic use of colony stimulating factors will be based on clinical judgment and may be appropriate in patients with a documented infection in the presence of severe granulocytopenia (granulocyte count less than 500/mm^3). Use of colony stimulating factors in clinically indicated situations should be consistent with product labeling and recorded on the concomitant medication form. The use of growth factors should follow published guidelines of the American Society of Clinical Oncology 2006 Update of Recommendations for the Use of White Blood Cell Growth Factors: An Evidence-Based Clinical Practice Guideline. J Clin Oncol 24(19): 1-19 AND American Society of Clinical Oncology/American Society of Hematology 2007 Clinical Practice Guideline Update on the Use of Epoetin and Darbepoetin J Clin Oncol 25(34): 1-17. (See [www.asco.org](http://www.asco.org) web site)

**10.5 Erythropoietin:** RBC support with erythropoietin can be used at the physician's discretion.

**10.6 Pneumocystis jirovecii pneumonia (PJP [PCP]) prophylaxis:** Pneumocystis jirovecii pneumonia has developed in patients when taking concomitant TMZ and steroids. This is of concern especially for lymphopenic patients. Prophylactic treatment is required for the concomitant RT/temozolomide of the study (cycle 1). See section 8.2.3 for details.

**10.7 Surgery:** If neurosurgical management is required for reasons not due to tumor progression, these procedures must be documented, including the indications for surgery, the surgical operative note and pathology report.

**10.8 Corticosteroid treatment:** Dosages and evaluation date of dexamethasone use must be recorded on concomitant steroid, anticonvulsant, and antiemetic medication form. Corticosteroids should be used in as low a dose as possible. At progression of disease, corticosteroid choice and dosages are at the discretion of the patient's physician.

**10.9 Treatment of fatigue:** Patients experiencing profound fatigue may use medications such as modafinil at the discretion of the treating physician.

## 11.0 TREATMENT EVALUATION

## 11.1 Objectives – (see section 2.1-3)

## 11.2 Imaging assessment

**11.2.1 Conventional MRI scans (Standard care):** Diagnostic MRI scans with and without contrast will be utilized to assess for response.

**11.2.2 sMRI (Research, 2 scans at week 0 (before treatment) and week 2):** 3-D whole brain MR spectroscopic imaging sequence (EPSI/GRAPPA) and the analysis program MIDAS (Metabolic Imaging Data Analysis System) were developed by [name] (scientific PI of U of Miami) in 2006 [31-42]. The scan will be done in 3T Siemens MR scanner (TIM/TRIO, Prisma, Skyra) or equivalent. Metabolite maps and their ratio maps will be calculated in MIDAS. Due to some degree of variability of Cho/NAA ratio between subjects, we will use the signal from contralateral normal white matter for normalization. We will use a web-based sMRI clinical interface to extract information from MIDAS to visualize the metabolite maps for efficient clinical workflow of the MIDAS results for busy clinicians and non-MRS experts. In addition, this web-based tool allows effective data sharing among imaging scientists and clinicians for consultation and storage of de-identified data sets (this sMRI clinical interface has been used at Emory (NCI U01 CA172027 & NCI R21 NS100244; Emory IRB00055973). sMRI studies will be obtained at the schedule outlined in section 7.1.

## 11.3 Response criteria

**11.3.1 Measurable Disease:** Measurable lesions with clearly defined margins by contrast-enhanced MRI scan beyond pseudoprogression period. We anticipate an extended period of pseudoprogression with dose escalation.

**11.3.2 Objective Status, To Be Recorded at Each Evaluation:** Unless progression is observed, objective status can only be determined when ALL measurable sites and lesions are assessed.

### 11.3.3 Response Definitions

**11.3.3.1 Complete Response (CR):** Complete disappearance of all measurable disease in contrast-enhancing MRI. No new lesions. No evidence of non-evaluable disease. All measurable lesions and sites must be assessed using the same techniques as baseline. Patients must be on no steroids.

**11.3.3.2 Partial Response (PR):** (Measurable disease only) Greater than or equal to 50% decrease under baseline in tumor volume [43] of all measurable lesions. No progression of evaluable disease. No new lesions. All measurable lesions and sites must be assessed using the same techniques as baseline. *The steroid dose at the time of the scan evaluation should be no greater than the maximum dose used in the first 8 weeks from initiation of therapy.*

**11.3.3.3 Stable Disease (SD):** Does not qualify for CR, PR, or progression. The designation of SD requires a minimum of 8 weeks duration (2 assessment of stable disease 8 weeks apart). All measurable sites must be assessed using the same techniques as baseline. The steroid dose at the time of the scan evaluation should be no greater than the maximum dose used in the first 8 weeks from initiation of therapy.

**11.3.3.4 Progressive Disease (PD):** 50% increase in the tumor volume of all measurable lesions over previous exam (over baseline if no decrease) using the same techniques as baseline, OR clear appearance of any new lesion/site, OR clear clinical worsening or failure to return for evaluation due to death or deteriorating condition (unless clearly unrelated to this cancer). NOTE: Increasing contrast enhancing disease in months 1-3 (potentially up to month 6) post-RT may represent pseudoprogression. For the current study, we anticipate that incidence of this phenomenon will be increased.

Because of difficulties in the interpretation of pseudo-progression on MRI, the first three post-RT/TMZ scans should NOT be used to declare progression. Progressive worsening on subsequent imaging studies usually distinguishes true progression from pseudoprogression. In particular, DSC perfusion imaging may be helpful at distinguishing true and pseudoprogression. If the rCBV map does not show evidence of increased perfusion in regions with increasing contrast-enhanced lesion(s), then pseudoprogression is favored and patient may be maintained on study. Subsequent increases up to 6 months post-RT will be evaluated on a case-by-case at a multi-disciplinary tumor board of the respective institution to assist in making a determination regarding true versus pseudoprogression and whether pathologic sampling would be beneficial. The date of progression will be backdated to when the changes were first observed in the case that the patient is later determined to have true progression.

**11.3.3.5 Regressive Disease (REGR):** (Evaluable disease only) Unequivocal reduction in extent of contrast as compared to baseline-enhancement or a decrease in mass effect as agreed upon independently by primary physician and quality control physicians; no new lesions.

**11.3.3.6 Unknown:** Progression has not been documented and one or more measurable sites have not been assessed.

**11.4 Best Response:** This will be calculated from the sequence of objective statuses. For patients with all disease sites assessed every evaluation period, the best response will be defined as the best objective status as measured according to section 11.5.

**11.5 Neurological Exam:** Although not used for determining response, it is useful to evaluate improvement in the neurologic exam, as compared with the baseline assessment, that should coincide with objective measurement of tumor size.

NEURO EXAM STATUS (compared to pre-treatment exam)	
Better	Must be on stable or decreasing dose of steroids
Same	Failure to qualify for better or worse
Worse	Include patients requiring increasing steroid doses to remain stable

**11.6 Performance Status:** Patients will be graded according to Karnofsky Performance Status (see Appendix 3).

**11.7 Time to Treatment Failure:** From date of registration to the date of first observation of PD (as defined in section 11.5), non-reversible neurologic progression or permanently increased steroid requirement (applies to SD only), death due to any cause, or early discontinuation of treatment.

**11.8 Overall Survival Time:** From date of definitive surgery or biopsy to date of death due to any cause.

**11.9 Progression Free Survival Time:** From date of definitive surgery or biopsy to date of progression (defined in section 11.3.3.4) or death. Once the real progression is confirmed from the subsequent scans, the first date exhibiting PD will be noted as the PFS time.

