Based on retrospective analysis of successive Brain Tumor Study Group trials, a fractionated dose of 60 Gy was determined to be optimal for GBMs [6]. A typical RT dosing regimen for the treatment of GBM involves treating a wide volume, including nonenhancing  $T_{2w}$ /FLAIR-hyperintense regions with margin, to a moderate dose (45-54 Gy), followed by a boost to the resection cavity plus any residual  $T_{1w}$ -CE abnormality with margin to a higher dose (60 Gy). A study using proton therapy for GBM found that patients not only tolerated doses up to 90 cobalt-gray equivalent (CGE), but also started to display a change in the pattern of recurrence with nearly all failures in regions receiving < 70 CGE [7]. Of note, TMZ was not used for this study. This result suggests that tumoricidal doses (in the 70+ Gy range) may have finally been achieved, with marginal failures now being due to growth of disease that had infiltrated into brain surrounding the initial contrast-enhancing portion of the tumor. This study also suggests that better definition of the brain volume most at risk for tumor recurrence may allow better targeting of these regions with higher doses leading to improved local control and overall patient outcomes. Combining RT dose escalation with concurrent/adjuvant TMZ may produce more toxicities, especially since the incidence of pseudoprogression after concurrent RT/TMZ is significantly higher than after RT alone. Pseudoprogression is the phenomenon where an early increase in volume of contrast enhancement is seen following treatment with RT/TMZ (usually within 3 months post-RT). This effect is indistinguishable from early true tumor progression by standard MR imaging, and is generally only distinguished by serial imaging over time, when this change either stabilizes/improves (pseudoprogression) or continues to worsen (true progression) without alterations in the therapy. Brandes et al. have reported that the overall incidence of pseudoprogression is on the order of 30% in patients treated with the Stupp regimen [8]; therefore, it follows that TMZ may also alter tolerance to dose-escalated RT. This concern has been somewhat allayed by Tsien et al. with their report that TMZ could be safely paired with dose-escalated intensity modulated RT [9]. Of note, no late grade III or greater CNS toxicities were seen with doses up to 75 Gy, and for doses above 75 Gy (7 pts at 78 Gy and 9 pts at 81 Gy), only 3 patients developed  $\geq$  grade III late CNS toxicities. Thus, it appears that dose-escalated RT may be safely paired with TMZ. Since previous results also suggest that very high radiation doses (70+ Gy range) shift the pattern of recurrence to the margins of the high dose irradiation zone [7], there is now a greater premium on defining further areas that may be at increased risk of recurrence that can potentially be boosted by these higher doses.

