### 14.2 Secondary Objectives

14.2.1 To determine whether the progression free survival at 1 year sMRI-guided, dose-escalated RT increases with newly-diagnosed GBMs. Subjects on this study will be followed for progression free survival (PFS) which is defined from the time of surgical resection to the time of either radiographic progression or death, whichever occurs first. While PFS actuarial curves will be assessed and compared to historical controls, we are particularly interested in comparing the 1-year PFS rate which, based on the control arm (receiving standard dose RT with TMZ) of recent GBM trials, is approximately 30% in historical cohorts [44-46].

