**14.5 Statistical analysis for survival endpoints:** The primary objectives are to determine the feasibility of this escalated protocol and the safety of increased doses in patients with GBM. We anticipate that 30 patients will provide us sufficient data to make these conclusions. Since survival analyses are exploratory objectives of this study, these endpoints are not used to determine accrual numbers for this study. The PFS of patients in this protocol will be compared with historical controls, and that data will be used to estimate the effect size for future power analyses. With a planned accrual of 30 subjects, the following power to detect potential improvements in 1 year PFS is as follows: 1-year PFS rate is expected to be 30-35% based on historical controls [44-46]. Our study will have 82% power to detect an improvement to a rate of 60% at  $\alpha=0.05$  using a two-sided test. Cox's proportional hazard regression model will be applied to model 1-year PFS outcome to test whether subjects treated with escalated RT doses guided by the sMRI demonstrate significantly higher PFS as compared to historical controls receiving standard treatment, controlling for other potential risk factors. Of note, calculations to determine the power to detect a certain PFS effect size based the number of patients we needed to determine feasibility and safety were presented above. However, this study was not actually powered based on PFS improvement.

**14.6 Statistical analysis of sMRI scans:** This study is mainly using pre-RT sMRI parameters to help define a region at high risk for recurrence that can be treated with higher doses of RT. Exploratory objectives will involve examining changes in absolute metabolite levels and metabolic ratios during RT that may be useful for adaptive radiation therapy (changing dose plan during early phase of RT). sMRI data will be evaluated both on a patient-wise basis and on a voxel-wise basis with utilization of deformable registration technique, as needed, to achieve good matching of maps across serially acquired scans.

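### The trial's 1-year PFS excludes settled early growth as an event, but the historical rate it is compared with is not required to be scored with an equivalent allowance

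*Combined protocol and SAP*

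**What the plan says.** **How progression is scored here.** Section 11.3.3.4 defines progression by a 50% volume increase, a clear new lesion or clear clinical worsening. It expects pseudoprogression to be more frequent with this regimen and so adds a study-specific restriction: "the first three post-RT/TMZ scans should NOT be used to declare progression". Further increases up to 6 months after RT "will be evaluated on a case-by-case at a multi-disciplinary tumor board of the respective institution". When progression is later judged real, "The date of progression will be backdated to when the changes were first observed". Section 11.9 repeats this for PFS: "the first date exhibiting PD will be noted as the PFS time".

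**What it is compared with.** Section 14.2.1 counts PFS "to the time of either radiographic progression or death, whichever occurs first" and sets the result against a 1-year rate that, "based on the control arm (receiving standard dose RT with TMZ) of recent GBM trials, is approximately 30% in historical cohorts". Section 14.5 says that the "1-year PFS rate is expected to be 30-35% based on historical controls", claims 82% power to detect 60% with 30 patients, and plans a Cox model against historical controls with adjustment for other risk factors. It also says that the study was not powered on PFS and that the comparison will supply an effect size for future power calculations.

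**What is absent.** The plan does not state how progression was scored in the control series, does not require a matching rule, and does not include an analysis of trial patients under any other rule.

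**The concern.** Section 1.0 says that standard MRI cannot separate pseudoprogression from early true progression, and that "the overall incidence of pseudoprogression is on the order of 30% in patients treated with the Stupp regimen". Consider a patient whose enhancement grows on the first or second scan after RT and then settles, with no clear clinical worsening. In this trial that patient remains progression-free. In a control series that accepted early enhancing growth as progression, the same patient would be an event. The two 1-year rates would then measure different endpoints, and the difference would favour the trial even if 75 Gy did nothing.

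Improved 1-year PFS is the only secondary objective (section 2.2.1). A scoring artefact could support that claim and would also pass into the effect size for the next study.

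**Working it through.** **1. The plan's own figure.** One-sample test of a proportion against a fixed rate, normal approximation, two-sided 5%, n = 30, alternative p1 = 0.60:

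power = Φ{ [ (p1 − p0)√n − 1.96√(p0(1 − p0)) ] / √(p1(1 − p1)) }

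- p0 = 0.35: 81.2%, close to the stated 82%.
- p0 = 0.30: 93.6%.

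The stated power thus treats the historical rate as a known constant near 35%. Both ends of the 30-35% range are carried below.

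**2. Does the three-scan bar by itself push progressions past year 1?** The inputs are MRI before odd-numbered cycles (section 7.1), 28-day cycles and a 4-6 week break (section 8.2), and RT starting no later than 50 days after resection (section 8.1.1). Assume 6 weeks of RT and no cycle delays.

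- The barred scans (before cycles 1, 3 and 5) fall about 0.9 to 5.1 months after RT.
- The fourth scan (before cycle 7) falls (4 + 24) to (6 + 24) = 28 to 30 weeks after RT, or 6.4 to 6.9 months.
- At the latest that is 7.1 + 6 + 6 + 24 = 43.1 weeks after surgery.

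A real progression can therefore be declared on the fourth scan, before one year, and backdated. For confirmed progressors the bar need not change 1-year status.

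**3. What remains.** Early growth that settles is never confirmed, so backdating never applies to it. Whether it counted in the control series is not documented. Let s be the share of pseudoprogressors scored as progression in the controls, and t the share of those who were really progression-free at 1 year. Then:

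shift = 0.30 × s × t

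Only the 0.30 comes from the protocol; s and t are assumptions.

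| | t = 30% | t = 40% | t = 50% |
|---|---|---|---|
| s = 0 | 0 | 0 | 0 |
| s = 25% | 2.25 points | 3.0 | 3.75 |
| s = 50% | 4.5 | 6.0 | 7.5 |
| s = 100% | 9.0 | 12.0 | 15.0 |

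**4. Effect on a claim of improvement.** Section 14.5 names no exact test, so this part is illustrative. Take an exact binomial test with n = 30 and the smallest cut-off whose upper tail is at most 2.5%: at least 15 of 30 against 30%, and at least 17 of 30 against 35%. For a regimen with no true effect, the chance of crossing the cut-off is P(X ≥ cut-off) at a true rate of p0 + shift:

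| Shift | Null 30%, at least 15/30 | Null 35%, at least 17/30 |
|---|---|---|
| 0 | 1.7% | 1.2% |
| 6 points | 8.2% | 6.1% |
| 9 points | 14.7% | 11.3% |
| 15 points | 35.5% | 29.2% |

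**The case against.** The strongest reply is that the bias is not shown to exist. The documents do not say how the control arms were scored; with a comparable allowance the shift is zero. This stands. What is established is undocumented comparability, together with the direction of the bias if the rules differ in the way described.

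A reader might infer that barring three scans simply delays progression and so inflates 1-year PFS. The documents do not support that: sections 11.3.3.4 and 11.9 backdate confirmed progression, and step 2 shows that the fourth scan comes before one year. A reader might also infer that no early growth ever counts. That too goes too far, because section 11.3.3.4 accepts clear clinical worsening as progression and its bar applies to scans only.

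Three further defences do not close the gap:

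- The plan fixes final PFS at year 1 as being beyond pseudoprogression (criteria for removal, section 14). This helps to classify trial patients but does not affect how the comparator was scored.
- Covariate adjustment in the Cox model cannot correct a different event definition.
- PFS did not size the study, and section 14.5 calls survival analyses exploratory. This limits the weight of the point, and the primary feasibility and safety conclusions are untouched. The plan nevertheless tests for higher PFS and reuses the estimate.

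**Conclusion.** The concern holds as a gap in comparability. Trial PFS follows a rule tailored to this regimen, and the literature rate set against it carries no matching requirement. If the controls counted some early enhancement as progression, the comparison favours the trial.

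The size cannot be determined from the documents. A 6-point shift (s = 50%, t = 40%, both assumed) would raise a nominal 1-2% chance of a false claim to about 6-8%, depending on the null and on a test that the plan does not name. The 15-point corner of the grid is tempting to cite as the likely bias. It requires every control pseudoprogressor to have been scored as progression and half of them to have been progression-free at one year, and nothing in the documents supports either value.

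The point deserves correction before analysis because it bears on the only secondary objective. It does not threaten the primary conclusions.

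**What to change.** In sections 14.2.1 and 14.5:

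1. State the progression rule of each historical series used, and prefer series with a comparable pseudoprogression allowance. Give one reference rate in both sections.
2. Keep the 11.3.3.4 PFS. Add a pre-specified sensitivity 1-year PFS from the scans already collected, in which the first scan meeting the volume or new-lesion criterion counts as progression, including the first three after RT. Where a control series' own rule can be reproduced, use that rule instead.
3. Report both rates with exact intervals. If they lead to different conclusions, describe the improvement over historical controls as dependent on the progression rule.
4. Carry both differences into future power calculations.
5. Reconcile the event wording: 11.3.3.4 includes clinical worsening, whereas 14.2.1 names radiographic progression or death.

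**Cost.** Plan wording and a second scoring of existing MRIs; no new scans or patients, and no change to how patients are managed. Reproducing an external rule takes reader time. A rule that needs steroid status may not be reproducible late in follow-up, because the section 7.1 table schedules no steroid documentation after adjuvant TMZ.

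**Downside.** The sensitivity rate is conservative, since any extra pseudoprogression from 75 Gy counts against the regimen. If the controls had an allowance, scoring without one can reverse the bias. It should therefore bound the main comparison and not decide it alone.

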### 3.3 Patient Selection - Inclusion Criteria:

- 3.3.1** Patients must have a newly-diagnosed glioblastoma or gliosarcoma that has been confirmed pathologically by a board-certified neuropathologist.
- 3.3.2** Patients must be  $\geq 18$  years of age.
- 3.3.3** Patients must be able to have MRI scans.
- 3.3.4** Patient must have the following lab values  $\leq 14$  days prior to registration:
  - WBC  $\geq 3,000/\mu\text{L}$
  - ANC  $\geq 1,500/\mu\text{L}$
  - platelet count of  $\geq 75,000/\mu\text{L}$
  - hemoglobin  $\geq 9.0$  gm/dL (transfusion is allowed to reach minimum level)
  - SGOT  $\leq 2.0x$  UNL
  - bilirubin  $\leq 2 \times$  UNL
  - creatinine  $\leq 1.5$  mg/dL
- 3.3.5** Patients must have a life expectancy of  $\geq 12$  weeks.
- 3.3.6** Patients must have a Karnofsky Performance Status (KPS)  $\geq 60$ .
- 3.3.7** Patients who are women of childbearing potential must have a negative pregnancy test documented  $\leq 14$  days prior to registration. This is not specific to dose escalation and is mandatory for standard care for patients being treated with radiation therapy. The cost of this test will be covered by standard of care.
- 3.3.8** Patients must be able to understand and provide written informed consent.
- 3.3.9** Both men and women, and members of all races and ethnic groups are eligible for this trial. Subjects will be approximately representative of the demographics of the referral base for the participating institutions.
- 3.3.10** Patient must be able to swallow capsules.
- 3.3.11** Patients must be willing to forego other cytotoxic and non-cytotoxic therapies against the tumor while being treated on this protocol.

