## 8.0 TREATMENT PLAN

### 8.1 Radiation Therapy

**8.1.1 Timing of Radiotherapy:** RT must begin  $\leq$  50 days from resection. Daily oral temozolomide will start together with the first day of radiation. RT may start on M-Th. Temozolomide is given every day during course RT (M-Su) up to a total of 42 doses (may halt as early as 40 doses if RT is completed prior to 42 dose course).

**8.1.2 Certification:** IMRT or VMAT technique will be used for all cases. To utilize IMRT or VMAT on this study, proper credentials are required. Previous certification by the Radiological Physics Center (RPC) for use of IMRT or VMAT on another protocol is acceptable.

**8.1.3 Radiation Energy:** Minimum photon energy is 6 MV with IMRT or VMAT plans designed and verified by simulation. Minimum SSD or SAD is 80 cm.

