### 14.3 Exploratory Objectives

14.3.1 To determine whether sMRI-guided, dose-escalated RT increases the overall survival of patients with newly-diagnosed GBMs. Subjects on this study will also be followed for overall survival (OS) which is defined from the time of surgical resection to the time of death. The OS actuarial curve and 1-year OS rate will be assessed and compared to historical controls. The 1-year OS rate of control arm patients on recent trials is approximately 66%

14.3.2 To determine whether sMRI data obtained after initiation of therapy (at 2 weeks after RT/TMZ start and prior to cycle 1 and 5 of adjuvant TMZ) will provide early evidence of GBM progression not seen on standard MRIs. Changes in sMRI parameters over time will be assessed to determine whether they will be able to predict development of recurrence. Global changes in sMRI parameters including to absolute metabolite concentrations or metabolic ratios will be examined to see if these factors may be an early marker of tumor recurrence. In addition, further assessments will be made on a voxel-wise basis to determine whether individual changes may be predictive of ultimate recurrence within particular voxels.

14.3.3 To determine whether performance on neurocognitive and quality-of-life (QOL) assessments in newly-diagnosed GBM patients treated with sMRI-guided, dose-escalated RT differ from historical controls. We will compare performance on neurocognitive and QOL assessments in our 30 subject cohort with performance by historical control cohorts from recent GBM trials (eg. RTOG 0525 and 0825) [45, 46]. Better performance may be attributable to better control of disease while worse performance may imply increased toxicity from the study treatment regimen.

**14.3 Accrual rate and numbers:** The anticipated rate of accrual will be 2-3 patients/month among three sites. This will allow consenting of 30 patients over a period of 1.5 years.

**14.3 Criteria for removal from trial:** All reasons for discontinuation of treatment must be documented.

**14.3.1** Progression of disease will be hard to determine due to pseudoprogression as defined in section 11.3. The final progression free survival will be determined at year 1, which is beyond pseudoprogression possibility.

**14.3.2** Patient may withdraw from study at any time for any reason.

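### PFS and OS are timed from surgery although patients can enter only later, and the historical rates they are compared with have no stated time origin, so the comparison cannot be shown to be like for like

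*Combined protocol and SAP*

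**What the plan says.** Section 11.9 runs PFS "From date of definitive surgery or biopsy to date of progression" or death. Section 11.8 runs OS "From date of definitive surgery or biopsy to date of death due to any cause". The statistical section words the start differently: PFS in 14.2.1, "which is defined from the time of surgical resection to the time of either radiographic progression or death, whichever occurs first", and OS in the exploratory objective 14.3.1, "which is defined from the time of surgical resection to the time of death". Time to treatment failure in 11.7 has another origin: "From date of registration to the date of first observation of PD".

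Entry comes after surgery. Inclusion criterion 3.3.1 reads "Patients must have a newly-diagnosed glioblastoma or gliosarcoma that has been confirmed pathologically by a board-certified neuropathologist". Laboratory values must be obtained in the 14 days before registration (3.3.4), and eligibility papers may follow pre-registration by up to 14 days (6.1.3). RT must start no later than "50 days from resection" (8.1.1).

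The comparators are historical: 1-year PFS of about 30% (14.2.1) or 30-35% (14.5), and 1-year OS of about 66% (14.3.1). The PFS rates are attributed to control arms of recent GBM trials. No section says when the clock starts in those arms. Section 14.5 plans a Cox model against historical controls and mentions neither delayed entry, nor a landmark, nor a re-based benchmark.

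**The concern.** A patient who dies between surgery and registration never joins the trial. For everyone who does join, that stretch is survived by design, yet it fills the first part of the 1-year window. For death this is certain. For progression it is likely but less strict, because the documents describe no on-study assessment before registration, but no criterion expressly excludes early regrowth.

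Whether this harms the comparison depends on the benchmark. If the historical rate counts 12 months from trial entry, the trial's 12 months from surgery contain less than 12 months at risk, and the trial gains some points without any treatment effect. If the historical rate also counts from surgery in patients enrolled later, both sides carry the same guaranteed time and it largely cancels. The documents do not allow a reader to tell which applies. The result matters beyond this trial because 14.5 intends the PFS data to supply the effect size for later power calculations.

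**Working it through.** **Inputs from the plan.** n = 30; two-sided alpha 0.05; historical 1-year PFS p0 = 30-35%; alternative p1 = 60%; stated power 82% (all 14.5); historical 1-year OS 66% (14.3.1).

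**Assumed, not in the documents.** A surgery-to-registration gap d of 14 to 50 days without events, a constant hazard, and historical rates that run from trial entry. The 50 days in 8.1.1 is the limit from resection to RT start, so it serves only as a ceiling.

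**1. The plan's own figure.** One-sample test of a proportion, normal approximation:

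power = Phi( (p1 - p0 - 1.96 × sqrt(p0(1 - p0)/n)) / sqrt(p1(1 - p1)/n) )

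With p0 = 0.35: (0.25 - 1.96 × 0.0871)/0.0894 = 0.887, so power is 81.2%, close to the stated 82%. With p0 = 0.30 the same formula gives 93.6%. The 82% therefore matches the 35% end of the stated range.

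**2. Shift in the no-effect rate.** If the historical rate S is counted from entry and the first d days after surgery are event-free, the 1-year rate counted from surgery is S^((365 - d)/365). For d = 50 and S = 0.30, the exponent is 315/365 = 0.863 and the result is 0.354.

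**3. Effect on a test.** The plan names a Cox model but gives no historical data set to run it on. As an illustration, take an exact one-sample binomial test at n = 30 with at most 2.5% in the upper tail. It rejects at 15 or more progression-free patients for null 30%, and at 17 or more for null 35%. The table gives the no-effect rate and the chance of reaching that limit.

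| Gap d (days) | PFS 30% reads as | P(15 or more of 30) | PFS 35% reads as | P(17 or more of 30) | OS 66% reads as |
|---|---|---|---|---|---|
| 0 | 30.0% | 1.7% | 35.0% | 1.2% | 66.0% |
| 14 | 31.4% | 2.6% | 36.4% | 1.9% | 67.1% |
| 21 | 32.2% | 3.2% | 37.2% | 2.3% | 67.6% |
| 28 | 32.9% | 3.9% | 37.9% | 2.9% | 68.1% |
| 35 | 33.7% | 4.7% | 38.7% | 3.5% | 68.7% |
| 50 | 35.4% | 7.1% | 40.4% | 5.3% | 69.9% |

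**4. Sensitivity to the hazard.** If risk is low early and rises (Weibull shape k), the exponent becomes ((365 - d)/365)^k. At d = 50, a 30% rate then reads as 37.0% for k = 1.3 and 40.8% for k = 2. The constant-hazard figures are not an upper bound.

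**5. The other case.** If the historical rates count from surgery in patients who enrolled with a similar delay, the shift from this source is about zero.

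**The case against.** The strongest reply is that no bias has been shown. A reader might infer that the surgery clock tilts the comparison with the 30% benchmark in the trial's favour. The documents do not support that, because they give no origin for the historical rates. This objection stands, and the point is conditional for that reason.

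Other parts of the reply also stand:

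- The gap is assumed. Registration comes before RT, so the average gap should be below 50 days, and the 7.1% and 5.3% figures belong to the extreme of the range.
- A reader might infer that anyone who progresses before registration is shut out. Sections 3.3 and 3.4 do not say so, and GTV3 in 8.1.4.4 provides for residual enhancement. Only death is excluded with certainty.
- The error rates come from a test the plan does not name. The baselines of 1.7% and 1.2% are low because of discreteness. With null 35%, the tail is still within 2.5% at a gap of 21 days.
- The registration origin in 11.7 does not contradict 11.8 and 11.9. Time to treatment failure includes early discontinuation of treatment, so registration is a natural start for it.
- A reader might infer that biopsy-only patients have no start date. Sections 11.8 and 11.9 give them one. The resection wording in section 14 is a mismatch to reconcile.
- PFS is secondary, OS is exploratory, and 14.5 says PFS did not set the sample size. A shift of 1 to 5 points is small beside the targeted rise of 25 to 30 points.

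The reply does not remove the gap in the plan. A comparison of 12-month rates needs the same 12 months on both sides, and the plan neither states nor ensures this.

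**Conclusion.** The documents establish three things: PFS and OS start at surgery or biopsy, registration can only follow, and neither the analysis nor the benchmark is adjusted for the interval. They do not establish that the result is biased. If the historical rates run from trial entry, the no-effect 1-year PFS is overstated by about 1 to 5 points (constant hazard, event-free gap of 14 to 50 days), and by more if early risk is low. OS is overstated by about 1 to 4 points. In the illustrative exact test with null 30%, the upper-tail error then rises from 1.7% to 2.6-7.1%. If the rates run from surgery with similar delay, the bias is near zero. Feasibility, safety, the stopping rule and the sample size are untouched. What is exposed is the PFS and OS comparison with historical controls and the effect size carried forward from it.

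**What to change.** 1. First establish the time origin of each historical rate and state it beside the figures in 14.2.1, 14.3.1 and 14.5. The order matters: moving the trial's clock to registration while the benchmark runs from surgery would bias the comparison against the trial.
2. If the origin is trial entry, start PFS and OS at registration for the historical comparison.
3. If the origin is surgery, keep surgery as the start, treat registration as delayed entry in the Kaplan-Meier and Cox analyses, and compare with a benchmark handled the same way. Otherwise, state that a similar entry delay is assumed on both sides. Delayed entry alone changes little when few events fall before the last patient has entered, so the matching of the benchmark is essential.
4. Use definitive surgery or biopsy as the wording in both section 11 and section 14.

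The cost is wording, a check of the cited trials and one extra analysis run, with no added patients or visits. Where the clock moves to registration, reported PFS and OS become slightly shorter.
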